4.9 Changes to Protocol

The protocol indicates that inclusion will be halted at sites that reach the 30% inclusion cap of total enrolment. This cap was changed to 15% in this SAP following request from the FDA.

5. Study Subjects

5.1 Disposition of Subjects

The number of subjects in each population will be tabulated by treatment arms as defined in section 4.5 and overall.

The study disposition of all randomized subjects will be summarized by randomized ventilation group and overall, with descriptive statistics for the ITT population. It will include the number of subjects who discontinued study treatment prematurely, or

withdrawn from the study completely, or stopped the follow-up for any reason upon investigator decision and patients who have completed study treatment or replaced due to technical failure in recording. The summary will also include reasons for discontinuing study treatment and termination of the study as recorded on the eCRF. The details of the 'other reason' will be included in the listing.

5.2 **Protocol Deviations**

The major protocol deviations will be summarized for each ventilation arm and overall, for the ITT population. The details will be listed by subject and ventilation arm.

Violations of inclusion and/or exclusion criteria, allocating patient to incorrect ventilation mode and deviations of other restrictions will be considered in the determination of the major deviations.

Protocol deviations will be defined as major or minor by the Sponsor during data review meetings before the interim and final database locks.

6. Demographic and other Baseline Characteristics

Descriptive statistics with respect to subject characteristics at baseline will be displayed for the ITT population(s). All subjects' characteristics at baseline will be described overall and by treatment group:

- Age
- BMI
- Race
- Ethnicity
- Height and weight
- Comorbidities and medical history
- Concomitant Treatment
- Reason for hospitalization (Cause of ICU admission)
- Smoking status

Physiology admission scores SAPS II, APACHE II and SOFA, Mechanical ventilation characteristics (INTELLiVENT-ASV, VC, PAC, VAC, SIMV, BiPaP, APRV, PS, ASV, Others) and Arterial Blood Gas analysis (PH, PaO₂, PaCO₂, HCO₃⁻, SaO₂, FiO₂, End-Tidal CO₂) at baseline will be summarized by treatment arms. Similarly, stratification information based on subject condition at inclusion will be tabulated by treatment arm if applicable. In addition, baseline characteristics will be presented by region (US vs EU). For categorical baseline variables, Fisher exact test will be used to test if there's a significant difference between US and EU whereas for continuous variables Mann-Whitney U test will be used to test for differences between the two populations. Results for these statistical tests will be mainly for informative purpose and no inference is intended to be made on these results.

7. Efficacy Evaluation

Efficacy evaluation will be performed on the ITT population. Values for optimal, acceptable, and sub-optimal ranges (maybe different for passive and spontaneous breathing ventilation periods) are listed in Values for optimal, acceptable and sub-optimal ranges of the study protocol.

7.1 Primary Efficacy Variable

The primary efficacy endpoint is a composite endpoint to assess the ability to keep the ventilation and oxygenation variables in optimal target ranges. The primary efficacy variable will be calculated as the percentage of time spent with **ALL** six variables in the optimal target ranges during the **7 days** after randomization:

- 1) Tidal volume (VT)
- 2) Maximum pressure (Pmax)
- 3) Oxygen saturation measured by pulse oximetry (SpO₂)
- 4) End-tidal partial pressure of carbon dioxide (PetCO₂)
- 5) Respiratory rate (RR) for spontaneous breathing subjects
- 6) Pmax-PEEP for passive ARDS subjects

The optimal and sub-optimal ranges are defined by pertinent guidelines for different clinical conditions including normal lungs, brain injury, ARDS, and chronic hypercapnia.

The primary efficacy variable will be expressed by median (interquartile range). Log transformation will be performed on the data before performing the 2 sample Z-test. Comparisons will use the 2 sample Z-test for log transformed variables. The P values <0.025 (one-sided, the hypothesis is that INTELLiVENT-ASV is better than "non-automated ventilation" on the Hamilton Medical Ventilators, in terms of efficacy) will be considered significant.

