8.3.2 Ventilation protocol in non-automated ventilation group

In order to standardize the non-automated ventilation process, Investigators will aim to keep the control arm (conventional non-automated ventilator) as close to the standard of care of the participating sites as possible.

General approach: The overall goals for the control arm ventilation protocol will be similar to those in the INTELLIVENT-ASV group including all recommendation available regarding gas exchanges targets, ventilator settings, protective ventilation targets, and weaning management (16, 32).

A. Passive subjects:

i. Ventilation mode

Any controlled mode will be possible such as volume control (CMV), pressure control (P-CMV), dual mode (APVcmv and APVsimmv), DuoPAP, SIMV, and P-SIMV. APRV will not be accepted. Tube resistance compensation (TRC) can be added.

ii. Ventilator settings

Respiratory rate will be adjusted according to PaCO_2 with a maximum of 35 Breaths/min.

Table 2: Management of pH and PaCO_2 :

$\text{pH} < 7.15$	$\text{pH}= 7.15 - 7.29$	$\text{pH}= 7.29 - 7.45$	$\text{pH} > 7.45$
Increase Respiratory rate up to 35 b/min and keep $\text{PaCO}_2 > 25$ mm Hg	Increase Respiratory rate up to 35 b/min and keep $\text{PaCO}_2 > 25$ mm Hg	Maintain VT around 6 mL/kg IBW in ARDS subjects and between 6 – 8 mL/Kg IBW for other subjects and maintain respiratory rate below 35 b/min.	Decrease respiratory rate but not below 6 /min
Consider NaHCO_3 If needed increase VT by 1 ml/Kg IBW or increase P_{INSP} by 2 cmH ₂ O with a maximum VT at 8 mL/Kg IBW for ARDS subjects and 10 mL/Kg IBW for other subjects. P_{PLAT} can be higher than 35 cmH ₂ O in case of extreme acidosis.	Consider NaHCO_3 If needed increase VT by 1 ml/Kg IBW or increase P_{INSP} by 2 cmH ₂ O with a maximum VT at 8 mL/Kg IBW for ARDS subjects and 10 mL/Kg IBW for other subjects. Keep $P_{\text{PLAT}} \leq 35$ cmH ₂ O.	Consider NaHCO_3 If needed increase VT by 1 ml/Kg IBW or increase P_{INSP} by 2 cmH ₂ O with a maximum VT at 8 mL/Kg IBW for ARDS subjects and 10 mL/Kg IBW for other subjects. Keep $P_{\text{PLAT}} \leq 35$ cmH ₂ O.	Consider NaHCO_3 If needed decrease VT by 1 ml/Kg IBW or decrease P_{INSP} by 2 cmH ₂ O with a minimum VT at 4 mL/Kg IBW for ARDS subjects and 5 mL/Kg IBW for other subjects.

PEEP will be set using PEEP/FiO₂ table, PEEP trial or transpulmonary pressure (based on the local hospital protocol).

PEEP will be kept in the range:

- 5-10 cmH₂O for normal lung subjects and COPD

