10.4.5 Analysis of Primary Endpoints

The objective of this study is to compare the efficacy and the safety of the investigational automated ventilation (INTELLiVENT-ASV) with a control ventilation group (conventional non-automated ventilation) in ICU subjects.

The hypothesis is that INTELLiVENT-ASV is better than conventional non-automated ventilation in terms of efficacy and safety.

Efficacy and safety endpoints are composite endpoints and are based on six variables that will be continuously recorded during the study period:

- 1) Tidal volume (VT)
- 2) Maximum pressure (Pmax)
- 3) Oxygen saturation measured by pulse oximetry (SpO2)
- 4) End-tidal partial pressure of carbon dioxide (PetCO2)
- 5) Respiratory rate (RR) for spontaneous breathing subjects
- 6) Pmax-PEEP for passive ARDS subjects

Endpoints will be measured up to seven (7) days after randomization

Values for optimal, acceptable and sub-optimal ranges have been defined according to previously published studies (13, 14) and current recommendations. These ranges are adapted to the subject clinical condition and may be different for passive and spontaneous breathing ventilation periods.

Table 6: Values for optimal, acceptable and sub-optimal ranges

Variable	Ref.	Subject condition	Subject activity	Sub-optimal low	Acceptable low	Optimal	Acceptable high	Sub-optimal high
SpO2 (%)	20	None	Passive or active	< 90	≥90 and <94	≥94 and ≤98 Or > 98 if FiO2= 21%	> 98	NA
SpO2 (%)		ARDS	Passive or active	< 85	≥85 and <88	≥88 and ≤96 or > 96 if FiO2= 21%	>96	NA
SpO2 (%)	20	Brain injury	Passive or active	< 90	≥90 and <94	≥94 and ≤98 Or > 98 if FiO2= 21%	> 98	NA
SpO2 (%)	20	Chronic hypercapnia	Passive or active	< 85	≥85 and <88	≥88 and ≤92 or > 92 if FiO2= 21%	>92 and ≤98	> 98
PetCO2 (mm Hg)		None	Passive	< 25	≥ 25 and < 34	≥ 34 and ≤ 44	> 44 and ≤ 49	> 49
PetCO2 (mm Hg)	19	ARDS	Passive	< 25	≥ 25 and < 32	≥ 32 and ≤ 42	> 42 and ≤ 52	> 52
PetCO2 (mm Hg)		None or ARDS	Active	NA	< 25	≥ 25 and ≤ 45	> 45 and ≤ 55	> 55
PetCO2 (mm Hg)		Brain injury	Passive or active	< 29	≥ 29 and < 34	≥ 34 and ≤ 39	> 39 and ≤ 44	> 44
PetCO2 (mm Hg)		Chronic hypercapnia	Passive or active	< 25	≥ 25 and < 35	≥ 35 and ≤ 55	> 55 and ≤ 60	> 60
VT (mL/Kg IBW)	21	None	Passive	< 4	≥ 4 and < 5	≥ 5 and ≤ 8	> 8 and ≤ 10	> 10
VT (mL/Kg IBW)	15, 27, 35	ARDS	Passive	< 4	≥ 4 and < 5	≥ 4 and ≤ 8	> 8 and ≤ 10	> 10
VT (mL/Kg IBW)		None, ARDS, or brain injury	Active	< 4	≥ 4 and < 5	≥ 5 and ≤ 10	> 10 and ≤ 12	> 12

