3.3.1 Randomization

The subjects will be randomized to either INTELLiVENT-ASV or Non-automated Ventilation using in a 1:1 ratio by a computerized central randomization system.

The two study arms will be stratified by subject condition at inclusion (normal lungs, ARDS, chronic hypercapnia, or brain injury) and by site to ensure balanced assignment for interventions at each site. The randomization scheme will be generated and maintained by the randomization module part of the electronic case report form (eCRF).

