4.1 Study Period and Participant Duration

4.1.1 Study Periods

Screening period: Starting the day of signature of informed consent up to and including the day before randomization. For subjects who are not randomized, the screening period will end on the day the subject is determined to be a screen failure.

Randomization (Day 0): After screening assessments are completed and subject's eligibility confirmed, the subject will be randomly assigned (1:1) to the automated ventilation with INTELLiVENT-ASV or to the non-automated ventilation. Randomization will be stratified according to the clinical condition at inclusion (normal lungs, ARDS, chronic hypercapnia, brain injury).

Intervention period (Day 1 – Day 27): From inclusion up to day of extubation (and not re-intubated within 48h after extubation), even if subjects remain on mechanical ventilation. During this period, subjects re-intubated within 48h after extubation will be kept in the study. Subject re-intubated beyond 48h will be considered as weaned from the ventilation.

The INTELLiVENT-ASV or control arm ventilator protocols will be continued until subjects are able to breathe unassisted for 48 hours, death, ICU discharge, study withdrawal, or day 28, whichever comes first.

Dropout could occur when patients are ventilated for less than 24 hours after inclusion because of unexpected death, transfer to another ICU, or withdrawal of informed consent. We expect a maximum of 5% of these cases.

Note a maximum of 5% of subjects are anticipated for which not 80% of mechanical ventilation time within the allocated randomized ventilation mode could be recorded due to documented technical reason. The recorded data will be used (with 'percent spent' calculated per the recorded time) for the primary analysis of the co-primary endpoints. As a sensitivity analysis, these values will be treated as missing data.

End of Study and participation duration (Day 1- Day 28):

Each enrolled subject will be followed for a maximum of 28 days. Prior to completion of study close out, all subject data must be captured and monitored in the eCRF.

The end of study visit should be completed at the time a subject completes the study. A subject will be considered to have completed the study for the following reasons:

- Subject completes follow-up visits as until day 28 as per investigational plan.
- Subject dies.
- Subject or legally authorized representative requests to be withdrawn from the study.

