4.4 Subgroup Definitions

Forest plots will be used to display results of primary endpoints and total duration of MV within the following subgroups listed below:

- Regions (US vs Europe)
- Study centers
- Gender

All efficacy tables and forest plots displaying primary and tertiary efficacy results will also be presented by treatment arm and for four groups based on subject condition at inclusion:

- Normal lungs
- ARDS
- Chronic Hypercapnia
- Brain injury

Additionally, forest plots to display primary and tertiary efficacy results by spontaneous and passive breathing subjects for the six ventilation and oxygenation variables will be reported:

1) Tidal volume (VT)

- 2) Maximum pressure (Pmax)
- 3) Oxygen saturation measured by pulse oximetry (SpO₂)
- 4) End-tidal partial pressure of carbon dioxide (PetCO₂)
- 5) Respiratory rate (RR) for spontaneous breathing subjects
- 6) Pmax-PEEP for passive ARDS subjects

Study centers will be pooled from largest to smallest until the pooled center had more than 5 subjects in each treatment group.

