7.4 Sensitivity Analyses

The Primary efficacy analysis will be repeated for the MITT population as sensitivity analysis. Other sensitivity analyses may be performed as appropriate. The Sensitivity analysis will be performed under MAR (Missing at Random) assumption. The Tipping point approach will be implemented to test the MAR assumption.

To check the sensitivity of the results of the primary efficacy analysis to the MAR assumption, MI based on models compatible with Missing Not At Random (MNAR) missingness mechanisms will be used. The approach below, using SAS PROC MI, will be considered:

The "shift imputation" approach: for missing values at a particular visit, it will be assumed that their expected value is smaller (shifted) by a specified amount than for the observed responses (implying that the missing values are more likely corresponding to smaller differences between arms than the observed ones). Different values of the shift will be explored to investigate the sensitivity of the results. This approach can be applied to data with arbitrary missing data patterns.

As other sensitivity analysis, the primary efficacy variable will be analyzed using an ANCOVA model, adjusting for region. All sensitivity analyses will be done at final analysis.

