8.2 Primary Safety Variable

The primary safety variable will be calculated as the percentage of time spent with **at least one** of the six variables in the sub-optimal target ranges during the **7 days** after randomization:

- 1) Tidal volume (VT)
- 2) Maximum pressure (Pmax)
- 3) Oxygen saturation measured by pulse oximetry (SpO₂)
- 4) End-tidal partial pressure of carbon dioxide (PetCO₂)
- 5) Respiratory rate (RR) for spontaneous breathing subjects
- 6) Pmax-PEEP for passive ARDS subjects

The primary safety variable will be expressed by median (interquartile range). Log transformation will be performed on the data before performing the 2 sample Z-test. Comparisons will use the 2 sample Z-test for log transformed variables. The P values <0.025 (one-sided, the hypothesis is that INTELLiVENT-ASV is better than conventional non-automated ventilation in terms of efficacy) will be considered significant.

Primary safety variable will be performed on the safety population.

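### Randomisation is stratified by condition and site, but neither co-primary test adjusts for them; if the strata are prognostic, the tests are conservative and a cheap efficiency gain is missed

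*SAP*

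**What the plan says.** SAP 3.3.1 sets the allocation scheme: "The two study arms will be stratified by subject condition at inclusion (normal lungs, ARDS, chronic hypercapnia, or brain injury) and by site". Protocol 6.2.1 says the same. SAP 4.1.1 is narrower: "Randomization will be stratified according to the clinical condition at inclusion (normal lungs, ARDS, chronic hypercapnia, brain injury", with no mention of site, and Protocol 8.1.2 agrees with that version.

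Both co-primary endpoints are compared without covariates. For efficacy, SAP 7.1 has "Log transformation will be performed on the data before performing the 2 sample Z-test". For safety, SAP 8.2 has "Comparisons will use the 2 sample Z-test for log transformed variables". The general rule at the start of SAP section 4 matches.

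The only covariate-adjusted treatment comparison is in SAP 7.4: "the primary efficacy variable will be analyzed using an ANCOVA model, adjusting for region. All sensitivity analyses will be done at final analysis". It adjusts for region, which is not a stratification factor. It covers efficacy only and is a sensitivity analysis. Its table (14.02.01.06) is not marked for either interim look.

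Condition at inclusion is used elsewhere: in by-condition tables and forest plots (SAP 4.4), in baseline tabulation (SAP 6) and, as pulmonary condition at visit 1, in the imputation model (SAP 4.8). Neither primary test uses it.

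**The concern.** Stratified randomisation balances the arms within strata, so stratum differences contribute little to the variability of the treatment difference. A two-sample Z-test does not take this into account: its standard error still contains the between-stratum variance. When the strata are prognostic, the reported intervals are too wide and the test rejects too rarely under the null.

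Prognostic strata are plausible here, though the documents do not demonstrate them. Protocol 10.4.5 says of the scoring ranges: "These ranges are adapted to the subject clinical condition and may be different for passive and spontaneous breathing ventilation periods". In Table 6 the optimal PetCO2 band is 34-39 mmHg in brain injury and 35-55 mmHg in chronic hypercapnia, and Pmax-PEEP counts only in passive ARDS. Sites may differ because control care is to stay "as close to the standard of care of the participating sites as possible" (Protocol 8.3.2).

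The same standard error also drives the interim efficacy and futility bounds and the conditional power that decides whether the trial grows from 254 towards 508. Compared with an adjusted test, the unadjusted one can withhold an increase or trigger an unneeded one. Both endpoints must succeed, so lost precision on either one matters.

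**Working it through.** **Inputs (SAP 3.4.1).** One-sided alpha 0.025; power 0.80; 1:1 allocation; looks at 128/192/254. Logit-scale differences are 0.58 (SD 1.5) for efficacy and 0.65 (SD 1.6) for safety. The correlation is -0.85, or 0.85 once both endpoints are oriented towards benefit. Efficacy bounds are 2.96/2.36/2.02 and interim futility bounds 0.44/1.34. The Protocol synopsis gives about 20 sites.

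**Assumption.** R² is the share of within-arm outcome variance explained by the strata. The documents give no value, so 0 to 0.30 is used, the same for both endpoints, with the stated SDs taken as total SDs.

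**1. Reproduce the plan.** With 127 per arm, √(2/127) = 0.1255.
- Efficacy drift: 0.58/(1.5 × 0.1255) = 3.08, giving fixed-design power Φ(3.08 − 1.96) = 0.869.
- Safety drift: 0.65/(1.6 × 0.1255) = 3.24, giving 0.899.
- Simulating both endpoints through the stated bounds with binding futility gives joint power 0.8007. The plan's 254 subjects and 0.80 power therefore reproduce.

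**2. Ideal balance.** Under stratified allocation the unadjusted Z has standard deviation √(1 − R²) instead of 1.
- Size at nominal 0.025 = 1 − Φ(1.96/√(1 − R²)).
- Interval width relative to the adjusted interval = 1/√(1 − R²).
- The adjusted test has its drift divided by √(1 − R²).

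For example, at R² = 0.20, √0.80 = 0.894, the width ratio is 1.118 and the size is 1 − Φ(2.19) = 0.0142. Joint powers are simulated (400,000 runs, group sequential, futility on either endpoint). A separate simulation agreed within about 0.002.

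| R² | Width ratio | Unadjusted size (fixed design) | Joint power, unadjusted | Joint power, adjusted |
|---|---|---|---|---|
| 0 | 1.000 | 0.0250 | 0.802 | 0.802 |
| 0.05 | 1.026 | 0.0222 | 0.810 | 0.823 |
| 0.10 | 1.054 | 0.0194 | 0.819 | 0.844 |
| 0.20 | 1.118 | 0.0142 | 0.841 | 0.888 |
| 0.30 | 1.195 | 0.0096 | 0.863 | 0.926 |

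**3. Sparse cells.** 20 sites × 4 conditions = 80 cells, and 254/80 is about 3 subjects per cell, so balance is imperfect. A subject-level simulation (about 24,000 runs) assumed 20 uneven sites with the largest at 15%, a condition mix of 45/30/10/15%, permuted blocks of 4 within site by condition, and R² split equally between the two factors. Sites with 5 or fewer subjects in an arm were pooled.

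| R² | Unadjusted | Adjusted, small sites pooled | Adjusted, all sites fitted |
|---|---|---|---|
| 0 | 0.802 | 0.796 | 0.781 |
| 0.05 | 0.804 | 0.810 | 0.798 |
| 0.10 | 0.815 | 0.834 | 0.827 |
| 0.20 | 0.827 | 0.870 | 0.872 |
| 0.30 | 0.841 | 0.903 | 0.911 |

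Entries are joint power. Single-endpoint fixed-design size for R² 0.05 to 0.30 was 0.023, 0.021, 0.017 and 0.014 unadjusted, and 0.024-0.026 adjusted with pooled sites.

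**4. Conditional power at the second interim.** With t = 192/254 = 0.756 and final bound 2.02, current-trend CP = Φ((Z/√t − 2.02)/√(1 − t)).
- CP = 0.33: Z = 0.869 × (2.02 − 0.440 × 0.494) = 1.57.
- CP = 0.80: Z = 0.869 × (2.02 + 0.842 × 0.494) = 2.12.

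At R² = 0.20 the adjusted Z is larger by 1/0.894. An unadjusted Z between 1.40 (1.57 × 0.894) and 1.57 is unfavourable on the planned test but promising on the adjusted one. An unadjusted Z between 1.89 (2.12 × 0.894) and 2.12 triggers an increase that the adjusted test would not need.

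**The case against.** The strongest reply is that nothing here is invalid. A pre-specified unadjusted test that controls type I error and meets its power target is a defensible choice, and 254 is not a wrong number. That stands, and it limits the point to an efficiency recommendation.

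R² is assumed. Scoring each condition against its own ranges could also shrink between-condition differences rather than create them. This stands too: at R² = 0.05 the realistic gain is only 0.6 points with pooled sites, and fitting all 20 sites would lose power. The cost side is equally small if sites are pooled.

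The power figures use the logit-scale planning values, whereas the SAP test is on log-transformed values. The powers therefore describe the planning model. The conservatism and relative gain depend on R² on whichever scale is analysed, so the direction does not change.

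If site is not a stratifier, its share of R² produces no conservatism of this kind, and the size figures above overstate it. A condition-only run at R² = 0.20 still gave size 0.021 and a gain of about 3 points.

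The pooling threshold behaves differently by look. In one simulation about 1.5 of 20 sites qualified to stand alone at 128 subjects, 6 at 192 and 9.5 at 254, so the rule must be specified per look. Sequential single-endpoint simulations of the adjusted test gave size 0.021-0.026 in one set of runs, with sites re-pooled at each look, and about 0.026-0.029 in another. This calls for a fuller specification and a check on size; it is not a reason to ignore the strata.

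By-condition efficacy results (Table 14.02.01.07) do reach both interim looks, but as descriptive output, not through the test.

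**Conclusion.** The point holds, on the condition that the strata are prognostic. Both co-primary tests ignore the factors used to randomise, and no planned treatment comparison adjusts for either. For R² of 0.05 to 0.30 the loss is about 1 to 6 points of joint power, with intervals about 3 to 20% too wide under ideal balance. At R² = 0 adjustment gains nothing and costs about 0.6 points with small sites pooled, or about 2 points with every site fitted. The error is on the safe side: type I error is not inflated and 0.80 power is retained. The sizes rest on the assumed R², equal for both endpoints, and on the assumed site and condition mix. The disagreement about whether site is a stratification factor does not depend on R² and needs correcting in any case.

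**What to change.** Before any unblinded interim look, amend the SAP so that:

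- The primary test of both co-primary endpoints is a linear model on the planned transformed scale, with arm, condition at inclusion (four levels) and site as main effects. The full site-by-condition cross-classification is too sparse.
- Small sites are pooled by a pre-specified rule. SAP 4.4 already has one that could be reused: "Study centers will be pooled from largest to smallest until the pooled center had more than 5 subjects in each treatment group". State whether pooling is redone at each look, and confirm the sequential size of the chosen rule by simulation.
- The model's Wald statistic is used at both interim looks, at the final analysis and for conditional power. The unadjusted Z-test becomes a sensitivity analysis.
- Site, pooled in the same way, is added to the imputation model in SAP 4.8, which already includes arm and pulmonary condition.
- SAP 4.1.1 and Protocol 8.1.2 are reconciled with SAP 3.3.1 and Protocol 6.2.1 on whether site is a stratification factor. If it is not, say so and justify keeping it in the model.

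The cost is SAP wording, standard code and a short simulation, using data already held from randomisation.
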